CT scan of chest, abdomen or pelvis, MRI, etc		X ^R			X ⁷	
Bone Scan					X ⁵	
EKG		X ^R	X			
Medication Diary			X ³			

1. SGOT, SGPT, total bili, Na, K, Cl, CO₂, BUN, creatinine, LDH, hemoglobin, calcium, albumin, total protein, magnesium, phosphorus and alkaline phosphatase.
2. For women of childbearing potential, ≤7 days prior to registration.
3. The diary must begin the day the patient starts taking the medication and must be completed per protocol and returned to the treating institution OR compliance must be documented in the medical record by any member of the care team.
4. +/- 3 days
5. If applicable
6. Research funded, cycles 1 and 2 only
7. Use the same method throughout the study. Follow-up scans to be performed every other cycle (8 weeks). Repeat measurements are required 8 weeks following an objective Response. See Section 11.0 for full RECIST criteria.
8. Every 4 months while on study, sooner should clinical symptoms indicate. These follow-up echocardiograms will coincide with restaging visits.
9. SGOT, SGPT, total bili, only and can be done at study site or locally and faxed.
- R Research funded (see Section 19.0)

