8.4 Guidelines for Management of Treatment Emergent Hepatotoxicity

Event	Dose Modification Algorithms
(A). ALT of $\leq 3.0 \times \text{ULN}$	Continue pazopanib at current dose with full panel LFTs ⁰ monitored as per protocol.
(B). ALT $>3.0 \times \text{ULN}$ to $\leq 8.0 \times \text{ULN}$ without bilirubin elevation (defined as total bilirubin ⁰ $<2.0 \times \text{ULN}$ or direct bilirubin $\leq 35\%$) and without hypersensitivity symptoms (e.g., fever, rash)	
Liver Event Monitoring Criteria:
 
(1) Continue pazopanib at current dose levels.
 
(2) Monitor subject closely for clinical signs and symptoms; perform full panel LFTs^a weekly or more frequently if clinically indicated until ALT/AST is reduced to Grade 1.

(C). ALT $>8.0 \times \text{ULN}$ without bilirubin elevation (defined as total bilirubin ^b $<2.0 \times \text{ULN}$ or direct bilirubin $\leq 35\%$) and without hypersensitivity symptoms (e.g., fever, rash)	
1st occurrence – Liver Event Interruption Criteria⁰:
 
(1) Interrupt pazopanib until toxicity resolves to \leqGrade 1 or baseline. Report the event to Novartis as an SAE within 24 hours of learning of its occurrence and complete the eCRF liver event forms. Make every reasonable attempt to have subjects return to the clinic within 24 to 72 hours for repeat liver chemistries and liver event follow up assessments.
 
(2) Liver imaging and other laboratory investigations should be considered as clinically appropriate.
 
(3) Monitor subject closely for clinical signs and symptoms; perform full panel LFTs^a weekly or more frequently if clinically indicated until ALT/AST is reduced to Grade 1.
 
(4) If the subject is benefiting from the study treatment, contact Novartis Study Physician for possible re-challenge. Re-treatment may be considered if ALL following criteria are met:
 
 - ALT/AST reduced to Grade 1 - Total bilirubin $<1.5 \times \text{ULN}$ or direct bilirubin $\leq 35\%$ - No hypersensitivity signs or symptoms - Subject is benefiting from therapy. 
Recurrence – Liver Event Stopping Criteria⁰:
 
Discontinue pazopanib permanently and monitor subject closely for clinical signs and symptoms; perform full panel LFTs^a weekly or more frequently if clinically indicated until ALT/AST is reduced to Grade 1. At the time of the recurrence, complete the eCRF liver event forms.

Event	Dose Modification Algorithms

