(D). ALT >3.0 x ULN with concomitant elevation in bilirubin ⁰ (defined as total bilirubin ≥2.0 x ULN; with direct bilirubin >35%) or with hypersensitivity symptoms (e.g., fever, rash).	
Liver Event Stopping Criteria⁰:
 
(1) Discontinue pazopanib immediately, report the event to Novartis as an SAE within 24 hours of learning of its occurrence, and complete the eCRF liver event forms. Make every reasonable attempt to have subjects return to the clinic within 24 hours for repeat liver chemistries and liver event follow up assessments.
 
(2) Consult a gastroenterologist / hepatologist, collect PK sample and perform the following assessments to identify potential co-factors:
 
 - Eosinophil count - Viral serology for hepatitis A, B, C and E, cytomegalovirus, Epstein-Barr virus (IgM antibody, heterophile antibody, or monospot testing) - Anti-nuclear antibody, anti-smooth muscle antibody, Type 1 anti-liver kidney microsomal antibodies. - Serum creatinine phosphokinase for possible muscle injury caused LFT elevation - Liver imaging 
-Consider toxicological blood screen for possible contributing chemical/medical entities
 
(3) Monitor subject closely for clinical signs and symptoms; record the appearance or worsening of clinical symptoms of hepatitis, or hypersensitivity, such as fatigue, nausea, vomiting, right upper quadrant pain or tenderness, fever rash or eosinophilia as relevant on the AE report form. Perform full panel LFTs^a weekly or more frequently if clinically indicated until LFTs are reduced to Grade 1.

For isolated total bilirubin ⁰ elevation without concurrent ALT increases (defined as ALT <3 X ULN).	
(1) Isolated hyperbilirubinemia (i.e., in the absence of elevated ALT or other signs/symptoms of liver injury) does not require dose modification. Pazopanib inhibits UGT1A1 and OATP1B1, which can cause elevation of indirect (unconjugated) bilirubin in the absence of liver injury..
 
(2) If bilirubin is >1.5 x ULN in the absence of ALT elevation, fractionation of bilirubin elevation should be performed. If bilirubin is >35% direct (conjugated), further evaluation for underlying cause of cholestasis should be performed.

- a. Full panel LFTs include: AST, ALT, alkaline phosphatase, GGT, and total bilirubin. Coagulation tests should be performed as clinically indicated.

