- b. Serum bilirubin fractionation should be performed if testing is available. If testing is unavailable and a subject meets the criterion of total bilirubin >1.5 x ULN, then the event should be promptly reported as an SAE.
- c. When a liver chemistry event meets the Liver Event Interruption Criteria, or Liver Event Stopping Criteria, blood samples should be obtained for PK and for clinical laboratory testing by the central laboratory (Liver Event Kits will be provided for this purpose).

Abbreviations: ALT alanine aminotransferase; AST aspartate aminotransferase; eCRF electronic case report form; IP investigational product; LFT liver function tests; PK pharmacokinetics; SAE serious adverse event; ULN upper limit of normal

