- a) Absorption – Pazopanib is absorbed orally with an absolute oral bioavailability range of 13.5 to 38.9% after an 800 mg dose, with a median absolute bioavailability of 21%. Plasma concentrations of pazopanib peak from 2 to 4 hours following single dose administration. Systemic exposure to pazopanib is increased when administered with food. Administration with a high-fat or low-fat meal results in an approximately 2-fold increase in AUC and C_{max} . Pazopanib should be administered at least one hour before or 2 hours after a meal. Administration of pazopanib as a crushed tablet increases the rate and extent of oral absorption relative to administration of the whole tablet. The crushing of the tablet increases AUC by 46% and C_{max} by approximately 2-fold, but decreases t_{max} by approximately 2 hours relative to administration of the whole tablet. Consequently, it is recommended not to crush pazopanib tablets.
 - b) Distribution – Binding of pazopanib to human plasma protein in vivo was greater than 99% with no concentration dependence. Pazopanib is associated with a small volume of distribution (9.2 to 131L).
 - c) Metabolism – In vitro studies demonstrate pazopanib is metabolized by CYP3A4 with a minor contribution from CYP1A2 and CYP2C8. Patients who have AST/ALT >3 X ULN and concurrent bilirubin >2 X ULN must permanently discontinue pazopanib. Use of pazopanib is not recommended in patients with total bilirubin >3 X ULN (regardless of any ALT) due to insufficient data with this severe impairment.
 - d) Elimination – Pazopanib has a mean half-life of 30.9 hours after administration of an 800mg dose. Elimination is primarily via feces with renal elimination accounting for < 4% of the administered dose.
- 15.16 **Potential Drug Interactions: CYP3A4 Inhibitors and Inducers:** Coadministration of pazopanib with strong inhibitors of CYP3A4 (e.g., itraconazole, atazanavir, indinavir, nefazodone, nelfinavir, saquinavir, telithromycin, voriconazole, ketoconazole, ritonavir, clarithromycin) increases pazopanib concentrations and should be avoided. Grapefruit juice should be avoided as it inhibits CYP3A4 activity and may also increase plasma concentrations of pazopanib. CYP3A4 inducers such as rifampin may decrease plasma pazopanib concentrations. Pazopanib should not be used if chronic use of strong CYP3A4 inducers cannot be avoided. Please see Appendix VI for a list of strong inhibitors and inducers of CYP3A4.

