- 15.26 Due to the similarity in nature of this agent to other VEGF inhibitors (bevacizumab, VEGF-trap, etc.) monitor for signs of bleeding, thrombosis and PE. Instruct patient to report any calf tenderness, shortness of breath, chest pain or bleeding immediately.
- 15.27 Cytopenias are common. Monitor CBC w/diff and instruct patient to report any unusual bruising or bleeding and/or signs of infection to study team.
- 15.28 Monitor LFT's. Patients who have AST/ALT levels > 3x ULN and concurrent bilirubin >2X ULN should permanently discontinue pazopanib. Patients with AST/ALT levels as above and mild hyperbilirubinemia (with suspected or known Gilbert's syndrome) should be monitored weekly while continuing pazopanib.
- 15.29 Cardiac side effects (CHF, MI, chest pain, etc). while rare can be serious and life threatening. Instruct patient to report any cardiac symptoms to study team immediately.
- 15.29a RPLS, CVA, and TIA are uncommon, but are life threatening. Instruct patient to report any neurological symptoms to the study team immediately.

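### Section 8.4 and Sections 15.15(c) and 15.28 give opposing dose instructions when ALT exceeds 3 x ULN, total bilirubin exceeds 2 x ULN, the direct share is at most 35% and there are no hypersensitivity symptoms

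*Combined protocol and SAP*

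**What the plan says.** Section 8.4 sorts liver events by ALT, bilirubin and hypersensitivity symptoms. Rows B and C are for patients without a bilirubin elevation. They define that as total bilirubin below 2 x ULN **or** a direct share of at most 35%. Both rows also require that there are no hypersensitivity symptoms.

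- Row B, ALT above 3 and up to 8 x ULN: "Continue pazopanib at current dose levels", with liver tests at least weekly.
- Row C, ALT above 8 x ULN: a first event is interrupted and re-challenge is possible under listed conditions. A recurrence is a permanent stop.
- Row D, ALT above 3 x ULN: immediate stop. The bilirubin condition is total bilirubin of at least 2 x ULN "with direct bilirubin >35%) or with hypersensitivity symptoms".

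Section 15.15(c), in the pharmacokinetic text, says: "Patients who have AST/ALT >3 X ULN and concurrent bilirubin >2 X ULN must permanently discontinue pazopanib". Section 15.28, in the nursing guidelines, says: "Patients who have AST/ALT levels > 3x ULN and concurrent bilirubin >2X ULN should permanently discontinue pazopanib". It then makes one exception, which begins "Patients with AST/ALT levels as above and mild hyperbilirubinemia" and is limited to suspected or known Gilbert's syndrome; those patients stay on drug with weekly monitoring. Neither sentence mentions the direct fraction.

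On the deciding test, 8.4 footnote b says: "Serum bilirubin fractionation should be performed if testing is available". If it is not available and total bilirubin is above 1.5 x ULN, the footnote asks for a serious adverse event report. It names no dose action. Section 4.0 footnote 9 limits the checks at weeks 2, 6 and 10 to "SGOT, SGPT, total bili, only and can be done at study site or locally and faxed". Section 4.0 footnote 1 and the full liver panel in 8.4 footnote a also list total bilirubin only.

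**The concern.** The same laboratory result leads to opposite actions depending on which page the investigator or nurse has open. Under row B the patient stays on the current dose; under Section 15 the patient loses the drug permanently. Following one text breaks the other, so this is more than a missing detail.

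The pattern can be expected with this drug. Section 8.4 itself notes: "Pazopanib inhibits UGT1A1 and OATP1B1, which can cause elevation of indirect (unconjugated) bilirubin in the absence of liver injury". Going one way risks continued dosing against a written hepatotoxicity stop. Going the other way risks ending treatment needlessly in a patient whose bilirubin rise is a transporter or enzyme effect.

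**Working it through.** There is no plan figure to reproduce. The check sets the rules side by side, treating each as a logical condition.

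**Step 1. Conditions** (ALT and total bilirubin, TB, in multiples of ULN; D = direct share; H = hypersensitivity symptoms)

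- No elevation, as 8.4 defines it: TB < 2 or D ≤ 35%.
- Row B: 3 < ALT ≤ 8, no elevation, no H.
- Row C: ALT > 8, no elevation, no H.
- Row D: ALT > 3 and either (TB ≥ 2 with D > 35%) or H.
- Section 15 stop, applied to ALT: ALT > 3 and TB > 2.

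**Step 2. Comparison over a grid.** ALT of 3.5, 8, 8.1 and 12; TB of 1.9, 2.0, 2.1 and 3.5; D of 20, 35 and 36%; H yes or no. That is 4 × 4 × 3 × 2 = 96 combinations.

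| Situation | 8.4 | Section 15 | Conflict |
|---|---|---|---|
| ALT 3.5 or 8; TB 2.1 or 3.5; D 20 or 35%; no H | Row B, continue | Permanent stop | Yes |
| ALT 8.1 or 12; TB 2.1 or 3.5; D 20 or 35%; no H | Row C, interrupt, re-challenge possible | Permanent stop | Yes |
| TB 2.1 or 3.5; D 36%, or H present | Row D, stop | Permanent stop | No |
| TB 1.9 or 2.0 | Row B, C or D | Not triggered | No |

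The conflicting combinations number 4 (ALT) × 2 (TB) × 2 (D) × 1 (no H) = 16, of which 8 fall in row B and 8 in row C. They are exactly the combinations with TB > 2, D ≤ 35% and no H. The count shows where the rules clash; it is not a probability.

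**Step 3. Direct bilirubin unavailable.** Take ALT > 3, TB ≥ 2, no H and D unknown. Rows B and C need D ≤ 35%, because TB < 2 fails. Row D needs D > 35%. No row can be assigned, and footnote b supplies a report but no dose instruction.

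**Step 4. AST.** Section 15 writes AST/ALT, while entry to every 8.4 row depends on ALT alone. If AST/ALT means either enzyme, a patient with AST > 3, ALT ≤ 3 and TB > 2 meets the Section 15 stop. Under 8.4 the same patient falls in row A, or, with ALT below 3 x ULN, can also be read into the isolated-bilirubin row. Neither stops the drug.

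**Step 5. Size.** The documents give no joint rate for ALT > 3, TB > 2 and D ≤ 35%. Table 79 gives separate rates (any-grade ALT increase 53%, any-grade bilirubin increase 36%), from which the joint rate cannot be derived. For illustration only, with the 39 patients of Section 16.22 and an assumed rate p, the expected number is 39p and the chance of at least one is 1 − (1 − p)^39:

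- p = 0.5%: 39 × 0.005 = 0.195; 1 − 0.995^39 = 0.178
- p = 1%: 39 × 0.01 = 0.39; 1 − 0.99^39 = 0.324
- p = 3%: 39 × 0.03 = 1.17; 1 − 0.97^39 = 0.695

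**The case against.** The strongest reply is that the two sections do not have equal standing. Section 8.0 is the dose-modification section, and 8.4 is its dedicated liver algorithm, with re-test, reporting and re-challenge rules. The reporting table in 10.51 repeats the criteria of rows C and D. By contrast, 15.15(c) is one sentence under metabolism and 15.28 is a nursing note. An experienced investigator would probably follow 8.4. That stands as the sensible reading, but no sentence says so, and 15.15(c) uses mandatory wording about a liver stop.

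The clash is also narrower than it may look. Section 15.28 says should, not must. Its Gilbert's exception gives the same action as row B for some patients with mainly indirect bilirubin, although mild is undefined and 15.15(c) has no such exception. In row C the immediate action, taking the patient off drug, agrees with Section 15; only the conditional return differs. Section 3.16 keeps out patients with raised bilirubin at entry, so the pattern has to develop on treatment. All of this limits the reach of the conflict without removing it, and the row B clash is untouched.

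A reader might infer three stronger things that the documents do not support:

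- **That the catch-all rows of 8.12, 8.2 and 8.3 create a second conflict**, since they discontinue at Grade 4 while row C can allow re-challenge. Those rows are residual categories beside a dedicated liver section. LVEF and proteinuria likewise have no row in 8.12 or 8.2 and are handled elsewhere in Section 8. A cross-reference would be tidy but is optional.
- **That direct bilirubin will not be measured because it is not scheduled.** It is an event-triggered test, footnote b asks for it where available, and nothing says the sites lack it. The gap is the missing dose action when there is no result.
- **That the primary endpoint is compromised.** Under 16.11 eligible, consented patients are evaluable once treatment has begun, and success is survival to 12 months. A permanent stop does not change how a patient is counted.

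**Conclusion.** The inconsistency is real and should be fixed. With ALT above 3 x ULN, total bilirubin above 2 x ULN, a direct share of at most 35% and no hypersensitivity symptoms, 8.4 continues or interrupts, while 15.15(c) requires and 15.28 advises a permanent stop. No precedence is stated. Two smaller gaps go with it: no dose action in 8.4 when direct bilirubin is unavailable, and no statement on whether AST alone triggers the stop.

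Few patients are likely to be affected. The 0.2 to 1.2 of 39 rests entirely on an assumed rate of 0.5% to 3% with no anchor in the documents, and should not be read as an estimate. The conclusion does not depend on it: one patient is enough to put a site in breach of one text or the other. The effect is on patient safety and consistent drug exposure; the primary analysis is not affected. Which rule is clinically right is for the clinical team, and the documents do not settle it.

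**What to change.** 1. State that 8.4 governs dosing for liver events, and replace the stop sentences in 15.15(c) and 15.28 with a reference to it. If the clinical team prefers the stricter rule, remove the direct-fraction test from 8.4 and from the table in 10.51 instead. Either way, say whether the Gilbert's exception is kept.
2. State whether AST above 3 x ULN also triggers the stop. Otherwise, pointing Section 15 to the ALT-only rows would silently drop the AST part of its rule.
3. If the direct-fraction test stays, require direct bilirubin whenever ALT is above 3 x ULN with total bilirubin of at least 2 x ULN, and interrupt the drug while the result is pending or unavailable.
4. Optionally, add a pointer to 8.4 in the tables of 8.12, 8.2 and 8.3.

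The cost is wording in 8.4, 15.15(c) and 15.28 (plus 10.51 under the stricter option), one extra blood test in the few patients who meet the trigger, and possibly a short interruption for them. Sample size, visit schedule and analysis do not change.

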9.0 Ancillary Treatment/Supportive Care

- 9.1 Antiemetics may be used at the discretion of the attending physician.
- 9.2 Blood products and growth factors should be utilized as clinically warranted and following institutional policies and recommendations. The use of growth factors should follow published guidelines of the American Society of Clinical Oncology (42) Update of Recommendations for the Use of Hematopoietic Colony-Stimulating Factors: Evidence-

Based, Clinical Practice Guidelines. J Clin Oncol Vol 24, No 19 (July 1), 2006: pp. 3187-3205

- 9.3 Patients should receive full supportive care while on this study. This includes blood product support, antibiotic treatment, and treatment of other newly diagnosed or concurrent medical conditions. All blood products and concomitant medications such as antidiarrheals, analgesics, and/or antiemetics received from the first day of study treatment administration until 30 days after the final dose will be recorded in the medical records.
- 9.4 Diarrhea: This could be managed conservatively with loperamide. The recommended dose of loperamide is 4 mg at first onset, followed by 2 mg every 2-4 hours until diarrhea free (maximum 16 mg/day). If grade 2 diarrhea consider dose reduction of pazopanib. If grade 2 diarrhea persists after 48 hours total treatment with loperamide discontinue pazopanib.

In the event of grade 3 or 4 diarrhea, the following supportive measures are allowed: hydration, octreotide, and antidiarrheals.

If diarrhea is severe (requiring intravenous rehydration) and/or associated with fever or severe neutropenia (grade 3 or 4), broad-spectrum antibiotics must be prescribed. Patients with severe diarrhea or any diarrhea associated with severe nausea or vomiting **should be hospitalized** for intravenous hydration and correction of electrolyte imbalances.

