7.4 Criteria for Treatment Discontinuation

- Patients who develop PD/recurrent disease while receiving therapy at the time of response assessments will be discontinued from active study treatment and go off protocol;
- Grade 3 or 4 toxicity requiring break from treatment and inability to re-initiate treatments with a ≥ 28 day delay;
- Completion of 12 months of therapy.

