All Other	Grade 2 or 3, if clinically significant Grade 4	Pazopanib	Omit until ≤ 1 Discontinue Pazopanib

* Located at

http://ctep.cancer.gov/protocolDevelopment/electronic_applications.ctc.htm

** Use the following to describe actions in the Action column:

- Omit = Treatment is not given for this cycle
- Hold/Delay = Treatment can be made up as part of this cycle
- Discontinue = Treatment is totally stopped

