8.2 Pazopanib-at time of retreatment

→ → Use the NCI Common Terminology Criteria for Adverse Events (CTCAE) version 4.0* unless otherwise specified ← ←			
CTCAE System/Organ/Class (SOC)	ADVERSE EVENT	AGENT	ACTION**
AT TIME OF RETREATMENT			
Investigations	Platelet count decreased Grade 3 or 4	Pazopanib	Hold until ≤ 2 then restart at next lower dose level. If no recovery to grade 2, discontinue
Investigations	Electrocardiogram QT corrected interval prolonged ≥ 500msec Grade 3	Pazopanib	Discontinue pazopanib
Renal and urinary disorders	Creatinine > Grade 3	Pazopanib	Hold until < 3 then restart at next lower dose level. If ≥ 3 recurs, dose reduce again until no dose can be given

→ → Use the NCI Common Terminology Criteria for Adverse Events (CTCAE) version 4.0* unless otherwise specified ← ←			
CTCAE System/Organ/Class (SOC)	ADVERSE EVENT	AGENT	ACTION**
Vascular disorders	Thromboembolic event DVT/PE Grade 3	Pazopanib	Hold and initiate anticoagulant. Decrease 1 dose level if 
 • Subject must have been treated at desired level of anticoagulation for at least 1 week • No Grade 3 or 4 or clinically significant Grade 2, hemorrhagic events have occurred while on anticoagulation treatment. Note: When treating with warfarin, INR S/B monitored within 3 to 5 days after any change in pazopanib dosing and then at least weekly until INR is stable. The dose of warfarin may need to be adjusted to maintain the desired level of anticoagulation.
	Grade 4		Discontinue pazopanib
	Arterial Thrombosis/Ischemia Any Grade		Discontinue pazopanib
Vascular disorders	Hypertension	Pazopanib	See table 8.3
Gastrointestinal disorders	Any GI bleed Grade 2-4	Pazopanib	Discontinue pazopanib
Respiratory, thoracic and mediastinal disorders	Any Pulmonary bleed Grade 2-4	Pazopanib	Discontinue pazopanib
Dermatology/ Skin	Dermatitis Grade 2 skin changes w/pain, limiting ADL's Grade3 severe skin changes w/pain Limiting self care ADL's	Pazopanib	Hold until ≤ 1 , then restart at next lower dose level. If recurrent. reduce by another dose level or discontinue Discontinue

→ → Use the NCI Common Terminology Criteria for Adverse Events (CTCAE) version 4.0* unless otherwise specified ← ←			
CTCAE System/Organ/Class (SOC)	ADVERSE EVENT	AGENT	ACTION**
All Other	Grade 2 or 3, if clinically significant Grade 4	Pazopanib	Hold until ≤ 1 Discontinue pazopanib

* Located at

http://ctep.cancer.gov/protocolDevelopment/electronic_applications.ctc.htm

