Anemia: No specific dose reduction rules are indicated for anemia unless due to hemorrhage or bleeding as noted above.	
Palmar-plantar Erythrodysesthesia Syndrome	
Grade 1 Minimal skin changes or dermatitis without pain (erythema, oedema, hyperkeratosis)	1. Continue pazopanib at present dose
Grade 2 Skin changes with pain; limiting instrumental activities of daily living (ADLs) (peeling, blisters, oedema, bleed, hyperkeratosis)	1. Hold pazopanib 2. Treat as clinically appropriate 3. Upon resolution to Level 1 or better restart pazopanib with a dose reduction to dose level -1 (if it was a full dose[800mg]) or one dose lower than the patient was receiving prior to developing the skin changes. 4. If recurrent consider a further dose reduction by 1 dose level until dose level -2. If patient has a Grade 2 toxicity on dose level -2, then consider stopping the drug.
Grade 3 Severe skin changes with pain and limiting self care ADLs	1. Discontinue pazopanib
Other Clinically Significant Adverse Events^a	
Grade 1	Continue pazopanib ; monitor as clinically indicated.
Grade 2 or 3, if clinically significant	Step 1. Interrupt pazopanib until toxicity resolves to \leq Grade 1. Step 2. Restart pazopanib dose-reduced by 200 mg(1 dose level) and monitor as clinically indicated.
Grade 4	Discontinue pazopanib and continue follow-up per protocol.

- a. AEs are graded according to NCI Common Terminology Criteria for Adverse Events v4.0 (NCI CTCAE v3)
- b. If ECHO does not show LVEF recovery after 2 weeks, repeat ECHO 2 weeks later.
- c. Symptoms may include: dyspnea, orthopnea, and other signs and symptoms of pulmonary congestion and edema.
- d. Hypertension detected in two separate readings during up to three consecutive visits
- e. Well-controlled blood pressure defined as SBP <140 mm Hg and DBP <90 mm Hg in two separate readings during up to three consecutive visits.
- f. Symptomatic hypertension defined as hypertension aggravated by symptoms (e.g., headache, light-headedness, vertigo, tinnitus, episodes of fainting) that resolve after the blood pressure is controlled within the normal range.
- g. Persistent hypertension is defined as asymptomatic hypertension after initially successful anti-hypertensive intervention.

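### Sections 9.4 and 8 give different pazopanib actions for persistent Grade 2 diarrhea, 9.4 gives none for Grade 3, and nothing says which section prevails

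*Combined protocol and SAP*

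**What the plan says.** Section 9.4 sits under supportive care and is the only dose instruction that names diarrhea. For Grade 2 it says "If grade 2 diarrhea consider dose reduction of pazopanib", and then "If grade 2 diarrhea persists after 48 hours total treatment with loperamide discontinue pazopanib". For the higher grades it says "In the event of grade 3 or 4 diarrhea, the following supportive measures are allowed: hydration, octreotide, and antidiarrheals". It goes on to cover antibiotics and hospitalization, but attaches no pazopanib action to Grade 3 or 4.

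Sections 8.12, 8.2 and 8.3 have no diarrhea row, so diarrhea falls into their residual rows. For a Grade 2 or 3 event, if clinically significant, 8.12 omits the drug until Grade 1 or less and 8.2 holds it until Grade 1 or less. Section 8.3 interrupts until Grade 1 or less and then says "Restart pazopanib dose-reduced by 200 mg(1 dose level) and monitor as clinically indicated". All three discontinue at Grade 4. The key printed under the 8.12 and 8.2 tables reads "Discontinue = Treatment is totally stopped" and lists this separately from omitting and from holding or delaying.

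Section 7.12 adds a general rule. Reductions go in 200 mg steps with roughly 10 to 14 days of monitoring at each level. If toxicity does not abate, the drug may be interrupted, reduced further, or both.

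**The concern.** A site managing Grade 2 diarrhea that has not settled on loperamide can open Section 9.4, Section 8 or Section 7.12 and find a different action in each. Read together, the rules also appear to run backwards: the lower grade, once persistent, meets a stop, while the higher grade meets a pause with a restart.

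What is at stake is consistency of treatment in a single-arm trial of 35 evaluable patients at three sites. Whether a patient with a common toxicity stays on drug could depend on which section the treating team consulted. That would make exposure and tolerability harder to interpret, and progression-free survival with them. It is also a safety instruction that staff need to be able to follow without guessing.

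**Working it through.** The plan states no figure on this point, so the main check compares the rules by grade.

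| Diarrhea | 9.4 | 8.12 / 8.2 residual row | 8.3 residual row |
|---|---|---|---|
| Grade 2, first seen | Consider reduction | If clinically significant: omit / hold until Grade 1 or less | If clinically significant: interrupt until Grade 1 or less, restart one level lower |
| Grade 2, persisting after 48 h of loperamide | Discontinue | Same as above | Same as above |
| Grade 3 | Supportive measures, no drug action | If clinically significant: omit / hold until Grade 1 or less | If clinically significant: interrupt, restart one level lower |
| Grade 4 | Supportive measures, no drug action | Discontinue | Discontinue |

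Three things follow.

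1. **Persistent Grade 2.** If *discontinue* in 9.4 means a total stop, it cannot be carried out together with the pause and restart in 8.3. Nor is it compatible with 7.12, whose monitoring period of 10 to 14 days per dose level is far longer than 48 hours.
2. **Grade 3.** Section 9.4 is silent on the drug, so Section 8 is the only source. The explicit restart is in 8.3; the residual rows of 8.12 and 8.2 give only the pause and its end point.
3. **Order of severity.** On the total-stop reading, the combined rules are stop (persistent Grade 2), pause and restart (Grade 3), stop (Grade 4). The text offers no reason for this order.

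**How many patients could be touched.** Inputs: Appendix VII (pazopanib arm of the RCC study, n = 290) gives diarrhea of any grade in 150, Grade 3 in 9 and Grade 4 in 2. The planned accrual is 39, of whom 35 are evaluable (Section 16.22).

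- Any grade: 150 / 290 = 51.7%.
- Maximum below Grade 3, at most: 150 − 9 − 2 = 139; 139 / 290 = 47.9%.
- Applied to 39 patients: 0.479 × 39 = 18.7, about 19.
- Applied to 35 patients: 0.479 × 35 = 16.8, about 17.

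The appendix does not split Grade 1 from Grade 2, and no section gives the share persisting beyond 48 hours of loperamide. The number affected therefore lies between 0 and about 19 of 39. The upper end would require every such case to be Grade 2 and persistent.

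**The case against.** The strongest reply is that Section 9.4 need not mean a total stop. The key is written for the Action column of the Section 8 tables, and 9.4 is prose outside any such column. Sections 8.3 and 8.4 in places write that the drug is permanently discontinued, which suggests the bare word may not always be final. If 9.4 means an interruption, it largely agrees with the Section 8 pause and the inversion disappears. This stands as a possible reading, so the conflict is stated conditionally. It does not remove the problem: the key is the protocol's only definition of the word, and a stopping instruction should not leave its meaning open.

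A second reply is that a rule naming diarrhea overrides a residual row, which in any case applies only if the event is clinically significant. That would settle Grade 2, although the protocol states no such precedence. It leaves Grade 3 without a drug action in 9.4, hence restartable through 8.3.

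A third reply is that the two triggers differ: 9.4 acts on failure of loperamide, 8.3 on grade. That is correct, and the Grade 3 side is best described as a gap in 9.4 rather than an express milder rule. The resulting order of actions still goes unexplained.

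A reader might also take Section 7.4 as evidence, since its toxicity criterion is "Grade 3 or 4 toxicity requiring break from treatment and inability to re-initiate treatments" after a delay and it does not list Grade 2 diarrhea. That list also omits mandatory stops in 8.12, such as arterial thrombosis of any grade, so it is not exhaustive and its silence proves little.

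**Conclusion.** The conflict is real and needs reconciling. It rests on two conditions: that *discontinue* in 9.4 carries its Section 8 meaning, and that the residual rows of Section 8 apply to diarrhea because no row names it. If the word means interruption, what remains is an undefined term and a missing Grade 3 and 4 drug action in 9.4.

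The number affected is between 0 and about 19 of 39 patients, if the Appendix VII rate carries over. A reader might want a narrower figure, but that would need an assumed Grade 2 share and an assumed persistence rate, and the documents give neither.

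A reader might also infer that the 12-month survival result is biased. The documents do not show this. Success is survival to 12 months from registration (Section 16.11). Patients who stop for reasons other than progression go to event monitoring (Section 13.3), and eligible patients are followed until death or for at least 2 years. Stopping drug does not in itself make a patient a failure, so any effect would run through reduced exposure, which cannot be quantified here. The supported consequence is inconsistent exposure and an ambiguous safety instruction across sites.

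**What to change.** Reconcile Section 9.4 with Sections 7.12, 8.12, 8.2 and 8.3:

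- State whether *discontinue* in 9.4 means an interruption or a total stop.
- Place one diarrhea row covering Grades 2, 3 and 4 in the Section 8 tables.
- Have 9.4 refer to that row for any pazopanib action and keep only supportive care itself.

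Which clinical rule stands is for the sponsor to decide; this review takes no position on it. The cost is a wording amendment and one added table row, with no extra visits, tests or patients.
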